# 9.3 **Primary Efficacy Endpoint**

The primary effectiveness endpoint is the comparison between the treatment groups of the quantification of actual vs planned tooth movements using weighted Peer Assessment Rating (PAR) index.

• Planned percentage reduction in PAR Score (Planned Improvement of Malocclusion [PIM])

In addition comparison between treatment groups will also be performed for:

- Actual percentage reduction in PAR Score (Actual Improvement of Malocclusion [AIM])
- Percentage of Accuracy of Outcome

Quantification and comparison of expressed and programmed tooth movements will be conducted using to measure orthodontic treatment need and outcome, the built-in weighted PAR analysis tool of 3Shape Ortho System software (K152086).

- 9.3.1 The weighted PAR scores for each Digital Study Model (DSM) would be compared as follows:
  - Planned percentage reduction in PAR Score (Planned Improvement of Malocclusion [PIM]) = PAR Score TS- PAR Score TP / PAR Score TS \* 100
  - Actual percentage reduction in PAR Score (Actual Improvement of Malocclusion [AIM]) = PAR Score TS- PAR Score TF / PAR Score TS \* 100
  - Percentage of Accuracy of Outcome = 100% [(|PIM -AIM|/|AIM|) \*100%]

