#### 12.2 Data Analysis

- 12.2.1 The Sponsor and Investigators are not blinded to the study data during the conduct of the trial, and may at periodic intervals analyze the data to assess study progress.
- 12.2.2 If nothing else is stated, descriptive statistics will be given for each variable in the clinical study and p-values may be complemented by confidence intervals as appropriate. When using the terminology descriptive statistics, it is meant that the number of subjects (N), mean, median, standard deviation (Sd), minimum (Min) and maximum (Max) values will be presented for continuous data and frequencies and percentages for categorical data.

- 12.2.3 All tooth movement data analyses will be performed using 3Shape Ortho System (K152086).
- 12.2.4 Three .stl files from each subject would be used for the analysis:
  - A pre-treatment STL file (TS) would be generated by scanning subject's pre-treatment intraoral scan taken before the start of treatment.
  - A planned or programmed STL (TP) file would be obtained from Archform Orthodontic Software System (K213916) after planned or programmed tooth movements have been made based on the treatment plan finalized by the digital lab and study Investigators.
  - The actual post-treatment STL file (TF) would be generated by scanning subject's post-treatment intraoral scan at the end of treatment.
- 12.2.5 Each STL file would convert into a Digital Study Model within the 3Shape Ortho System software to standardize the analysis.
- 12.2.6 Each DSM would be segmented using the "auto segmentation tool" of the software to demarcate each tooth separately.
- 12.2.7 This would be followed by Peer Assessment Rating (PAR) index to measure orthodontic treatment need and outcome (Richmond, 1992). This would be done using the built-in weighted PAR analysis tool of 3Shape Ortho System software. The PAR index will be performed by an external evaluator.
- 12.2.8 The weightage for each component of the PAR index would be set as: maxillary and mandibular anterior segment alignment x 1; buccal occlusion x 1; overjet x 6; overbite x 2; centerline x 4; following the ABO guidelines. The weighted PAR scores for each DSM would be compared as follows:

The PAR Score values for  $T_S$ ,  $T_P$ , and  $T_F$  will be transferred to the eCRF and the following will be calculated:

- Planned percentage reduction in PAR Score (Planned Improvement of Malocclusion [PIM]) = PAR Score TS- PAR Score TP / PAR Score TS \* 100

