- Actual percentage reduction in PAR Score (Actual Improvement of Malocclusion [AIM]) = PAR Score TS- PAR Score TF / PAR Score TS \* 100
- Percentage of Accuracy of Outcome = 100% [(|PIM AIM|/|AIM|) \*100%]

Statistical analysis comparing the two treatment groups using the Wilcoxon rank sum test will pe performed. A two-sided p-value below

5% will be regarded as statistically significant. The null hypothesis of the study is that there is no difference between the two groups.

- 12.2.9 Additional comparisons between treatment groups may be performed and p-values presented using the Wilcoxon rank sum test. Wilcoxon signed rank test may be used for analysis within treatment groups over time.
- 12.2.10 Calculation of Spearman's rank correlation coefficients will be performed to elucidate the relationships between the accuracy of outcome with treatment duration, number of aligners, subject pain levels, and overall subject and doctor satisfaction for each group.
- 12.2.11 All methods used in this clinical study have been previously published and reviewed (Griffith 2021, Grünheid 2022). All data in this clinical study will be analyzed by an independent contractor to remove bias. Any adjustments or modifications to these methods will be duly documented and reported.

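### The accuracy score divides by the achieved change, so it is undefined when PAR does not change and, at equal planned change, it ranks the most worsened subjects highest

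*Combined protocol and SAP*

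**What the plan says.** Section 9.3 words the primary efficacy endpoint as a between-group comparison of actual with planned tooth movement on the weighted PAR index. Section 9.3.1 builds it from three PAR scores per subject, at start (TS), as planned (TP) and at the end (TF):

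- "Planned percentage reduction in PAR Score (Planned Improvement of Malocclusion [PIM]) = PAR Score TS- PAR Score TP / PAR Score TS", times 100.
- "Actual percentage reduction in PAR Score (Actual Improvement of Malocclusion [AIM]) = PAR Score TS- PAR Score TF / PAR Score TS", times 100.
- "Percentage of Accuracy of Outcome = 100% [(|PIM -AIM|/|AIM", closed by a multiplication by 100%.

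Section 12.2.8 repeats the third formula with the same denominator ("Percentage of Accuracy of Outcome = 100% [(|PIM AIM|/|AIM"). On testing it says: "Statistical analysis comparing the two treatment groups using the Wilcoxon rank sum test will pe performed". Section 12.2.10 also uses the score in Spearman correlations, to describe "relationships between the accuracy of outcome with treatment duration, number of aligners", pain and satisfaction.

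Neither section says what to do when AIM is zero or negative.

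**The concern.** Accuracy against a plan is normally scaled by the plan, which is fixed before treatment. Here the scale is the outcome itself. A subject with no net improvement has no value, and a small achieved change of either sign inflates the score.

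This is the only listed measure that joins plan and result in one score: PIM is settled before treatment and AIM ignores the plan. Both analyses applied to it use ranks, so a wrong order goes straight into the result.

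Zero net change is possible even when some teeth move as planned. The component weights in section 12.2.8 are "overjet x 6; overbite x 2; centerline x 4", with anterior alignment weighted 1. A one-unit rise in overjet therefore adds 6 points and cancels 6 points of alignment gain, giving AIM=0.

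The gap could also be filled late. Section 12.2.1 leaves the sponsor and investigators unblinded and says they "may at periodic intervals analyze the data to assess study progress". A rule for AIM=0 chosen during or after the trial could be chosen knowing its effect.

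**Working it through.** **Inputs and reading.** The formulas are those of 9.3.1 and 12.2.8. The operator after the first 100% is lost in the extracted text and is read as minus. PIM and AIM are read as (TS-TP)/TS x 100 and (TS-TF)/TS x 100. Neither reading is counted as an error. The documents give no baseline PAR scores, so all PAR values below are assumed. The plan gives no figure for this measure to reproduce. Its one design figure, 23 per arm (12.1.2: SD 1, difference 1, 90% power, two-sided 5%), does reproduce: a two-sample t-test needs 22.02, rounded up to 23. It serves below only as an arm size.

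**Step 1, simplify.** PIM-AIM = 100(TF-TP)/TS and AIM = 100(TS-TF)/TS. TS cancels in the ratio, so Accuracy = 100 - 100 x |TF-TP|/|TS-TF|. The rest takes PIM>0.

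**Step 2, AIM=0.** TF=TS makes the denominator zero, so the score is undefined for any plan.

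**Step 3, worsened subjects.** Let w=|AIM| with AIM<0. Then |PIM-AIM| = PIM+w and Accuracy = 100 - 100(PIM+w)/w = -100 x PIM/w. This rises towards 0 as w grows. On a grid of integer scores (TS 1 to 39, every TP below TS, TF from TS+1 to TS+59), the more worsened subject scored higher in 45,240 of 45,240 adjacent pairs.

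**Step 4, worsened against improved, at equal PIM.** An improved subject with AIM=a and 0<a<PIM scores 200 - 100 x PIM/a. The worsened subject outranks this one if and only if a < PIM/2 and w > a x PIM/(PIM-2a). At PIM=80:

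- a=5: w above 5 x 80/70 = 5.7
- a=10: w above 10 x 80/60 = 13.3
- a=20: w above 20 x 80/40 = 40
- a=25: w above 25 x 80/30 = 66.7
- a=40 or more: never

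A subject who reaches at least half of plan always outranks a worsened one.

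**Step 5, exact scores for TS=20, TP=4 (PIM 80%).**

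| TF | Result | As printed | PIM as denominator |
|---|---|---|---|
| 12 | 40% better | 0 | 50 |
| 16 | 20% better | -200 | 25 |
| 18 | 10% better | -600 | 12.5 |
| 20 | no change | undefined | 0 |
| 23 | 15% worse | -533 | -18.75 |
| 24 | 20% worse | -400 | -25 |
| 40 | 100% worse | -80 | -125 |

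With milder scores, TS=12 and TP=4: TF=11 gives -600, TF=12 is undefined and TF=14 gives -400, against 12.5, 0 and -25 with |PIM|.

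**Step 6, count of reversed pairs, TS=20, TP=4.** Improved TF 13 to 19 against worsened TF 21 to 40 gives 7 x 20 = 140 pairs, of which 72 are reversed. Improved TF 4 to 12 gives none. With |PIM| none is reversed for improved TF 0 to 19. These are possible score pairs, not expected frequencies.

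**Step 7, sensitivity of power under assumed inputs.** 3,000 simulated trials per setting; integer TS 6 to 24; TP 20% of TS; AIM of subjects who track the plan distributed N(65, 20); 30% non-trackers in the test arm and none in control; two-sided 5% Wilcoxon. Power in percent at 23 / 50 per arm:

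| Non-tracker AIM | Printed, undefined dropped | Printed, AIM=0 ranked lowest | PIM as denominator | AIM alone |
|---|---|---|---|---|
| N(30, 15) | 29 / 56 | 31 / 59 | 30 / 59 | 31 / 58 |
| N(0, 15) | 29 / 58 | 40 / 74 | 40 / 74 | 40 / 74 |
| N(-20, 25) | 36 / 66 | 41 / 73 | 42 / 74 | 42 / 74 |

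Dropping undefined values costs 1 (30-29) to 16 (74-58) points against |PIM|. Ranking AIM=0 lowest stays within about 2 points.

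**The case against.** **The reversal hardly moves the test.** Stands for power: with AIM=0 ranked lowest, Step 7 shows almost no difference. Reversed subjects lie below half of plan and already rank low. The larger losses need undefined values to be dropped, which the plan does not say, and the 16 points come from centring non-trackers on AIM=0.

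**The reversal needs equal PIM.** Stands. With PIM 20 and AIM -10 the score is -200; with PIM 80 and AIM -20 it is -400, so there the more worsened subject does score lower. The pooled ranks mix different plans.

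**AIM at or below zero may be rare.** Possible. Refinement is allowed (4.3.3), completion requires the investigator to judge that a retainer can be ordered (8.9.3), and severe non-compliers can be withdrawn (8.10.1). A PAR score that doubles is extreme for mild malocclusion. None of this excludes AIM=0.

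**There are safeguards.** Section 12.2.11 names an independent contractor, requires changes of method to be documented, and says the methods are published. The cited studies were not available, so whether they use this denominator is unchecked. None of these provisions supplies a value at AIM=0.

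**Accuracy is an additional comparison.** Correct: 9.3 places PIM directly under the primary endpoint and lists AIM and accuracy as further comparisons. AIM is unaffected.

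**A rule for AIM=0 would be enough.** It would recover nearly all of the simulated loss, but would leave worsened subjects in reverse order. The new denominator does re-rank some improved subjects: with TS=20 and TP=12, TF=8 and TF=16 score 66.7 and 0 as printed, but 50 and 50 with |PIM|. That should be stated openly.

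**Conclusion.** The formula is wrong as written in both sections. It has no value at AIM=0, and for PIM>0 it orders worsened subjects backwards at equal PIM. Some worsened subjects also score above subjects who improved by less than half of plan. These results are algebra and depend only on the reading of the formulas. If the lost operator were not a minus, the quantity would be an error percentage with the same faults: at PIM=80 it would be 900 for AIM=-10 but only 180 for AIM=-100.

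The damage is confined to the accuracy comparison and its correlations. A deficit in actual improvement would still show in the AIM comparison, whose simulated power is within about 1 point of the |PIM| version. The effect on this trial cannot be computed, because the frequency of AIM at or below zero is not given; the power figures illustrate assumed inputs only. It should be corrected before outcomes are examined, but it does not invalidate the trial.

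**What to change.** In 9.3.1 and 12.2.8, replace the denominator by |PIM|:

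Accuracy = 100% - (|PIM-AIM|/|PIM|) x 100%, which equals 100% - (|TF-TP|/|TS-TP|) x 100%.

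For PIM>0 this is 0 at AIM=0 and falls steadily as the result falls short of plan or worsens. Add two statements:

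- Subjects with PIM=0 (TS=TP, known before treatment) are left out of this measure and counted by arm. Eligibility does not change.
- Overshoot beyond plan is scored as inaccuracy by design. At equal PIM, a worsened subject can outrank an improved one only if the improved subject's AIM exceeds 2 x PIM.

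The cost is one denominator and these short statements in two places, made before outcomes are examined. The TS, TP and TF scores are already recorded in the eCRF, so no new data are needed.

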# 9.4 Secondary Efficacy Endpoint

The secondary endpoint of this study will be to assess overall subject and dentist (Investigator) satisfaction with their treatment. This will be assessed through a questionnaire provided to both the dentist and the subject when treatment is completed. For this endpoint, a rating scale (1 very satisfied - 10 very unsatisfied) is used.

- 9.4.1 Doctor satisfaction with treatment results: "How satisfied are you with the results obtained?" (1 very satisfied 10 very unsatisfied).
- 9.4.2 Subject satisfaction with treatment results: This question is directed to the subject "How satisfied are you with the results obtained?" (1 very satisfied 10 very unsatisfied).

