EFFECTIVENESS ASSESSMENTS	Efficacy of Nighttime Aligners (worn 10-12 hours per day or night) will be assessed by demonstrating no statistically significant difference between expressed tooth movement versus programmed tooth movement at the end of treatment when compared to the Daytime aligners (worn 20-22 hours day/night). Quantification and comparison of expressed and programmed tooth movements will be conducted using Peer Assessment Rating (PAR) index to measure orthodontic treatment need and outcome, using the built-in weighted PAR analysis tool of 3Shape Ortho System software.
SAFETY ASSESSMENTS	The primary safety endpoint of the study will be the incidence of (device or dental) related AEs associated with the planned investigational treatment, as well as the occurrence of SAEs. Additionally, safety will be assessed through a post-treatment questionnaire administered to the subject asking about subject perceived comfort during treatment. Results will be quantified using a visual analogue scale. Both numerical values and a Wong Baker face scale will be used.
INCLUSION CRITERIA	
 
For inclusion in this clinical study subjects must meet all of the following criteria: 
 
Subject willing to participate in the clinical study and able to understand the content of the clinical study.
 
 
 
Subject must have permanent dentition (i.e. all second molars).
 
Subject must be 12 years of age or older.
 
Subject must be able to provide and sign consent for themselves, without requiring consent to be given by a legally authorized representative. Parental consent is also required for all participants who are not of the legal age to provide consent themselves (based on participant state of residence).
 
The subject requires correction of teeth without planned extrusive movements on either or both arches.
 

	
 
The subject has no greater than 5 mm of crowding and/or spacing (based on estimation by Investigator).
 

	
 
The subject does not require planned correction of molar tooth positions, posterior bite or molar classic relationship corrections. Subjects with Class II or Class III malocclusions requiring posterior bite / class correction are not eligible.
 

	
 
Subjects without prior orthodontic treatment within the past 18 months.
 

	9. Subjects who are periodontally stable.
	10. Subjects without a known history of plastic allergies.

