#### 1.2 Secondary Objectives:

The secondary efficacy objective of this study will be to assess overall dentist and subject satisfaction with the treatment.

Safety will also be assessed through subject questionnaire during and after treatment.

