# 7. RISKS AND BENEFITS OF PARTICIPATION

#### 7.1 **Risks**

- 7.1.1 The Sponsor has not identified any additional risks by participation in this clinical study. However, there are some risks that have an increased probability of occurrence with a reduced wear time aligner regimen including:
  - Reduced wear time causes teeth to shift while aligner is not worn; treatment takes longer than expected → Treatment Delay
  - Only wearing aligners for 10-12 hours per day can lead to greater subject discomfort when aligners are worn → Subject Discomfort
- 7.1.2 Additionally, there are risks associated with orthodontic treatment in general, including:
  - Discomfort: There may be some discomfort due to wearing an aligner for the first time, as the mouth is very sensitive. As the teeth move, often some discomfort is to be expected, however this usually wears off in a couple of days after each aligner tray

change. Aligners may cause irritation to the surrounding cheeks and lips.

- Allergy: Although rare, some people may be allergic to the plastic in aligners. If the subject knows that they have a plastic allergy or sensitivity, they should notify the Investigator prior to starting aligner therapy. Subject with known allergies to plastic materials are not eligible to participate in this clinical study. If an allergy to the aligner occurs, the Sponsor and/or the Investigator may recommend that treatment be paused and continued using alternative methods.
- Cavities: The surface of teeth may become weaker, and may have more cavities. Excellent oral hygiene will help to prevent this from happening during treatment.
- Resorption: The roots of teeth may become shorter or weaker during treatment. The Sponsor and/or the Investigator may recommend that treatment be paused if this process called root resorption occurs.
- Tooth movement not tracking according to the prescribed treatment plan: This can be caused by several factors; the top factor being subject compliance in wearing aligners the required number of hours per day/night. Treatment time may take longer than expected, or final outcomes may be different than what was planned when aligners are not worn as prescribed.
- X-ray: Standard procedures will be used i.e., all attempts to limit X-ray exposure will be made during the clinical study, including proper shielding.

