**CONFIDENTIAL:** The information in this study protocol is strictly confidential and is available for review to Investigators, study center personnel, the ethics committee, and the health authorities. It will not be disclosed to third parties without written authorization from the Sponsor, except to obtain informed consent from persons receiving the study treatment. Once the protocol is signed, its terms are binding for all parties.

- 8.3.5 The study aims to collect the following data at the following time points:
  - Intraoral scans of the subject prior to the start of treatment (Ts) and end of treatment (TF).
  - X-ray (PAN, CBCT, CEPH, and/or FMX) prior to the start of treatment (Ts) and at the end of treatment final visit (TF).
  - Intraoral and extraoral photographs prior to the start of treatment (Ts), at every check-in visit, and end of treatment final visit (TF).
  - Completed visit worksheet at initial aligner visit (TS), scheduled monthly check in visits (4-6 week intervals: T1, T2, T3, T4, etc.), and final aligner visit (TF).
  - Completed subject questionnaire at check in visits (4-6 week intervals: T1, T2, T3, T4, etc.),
  - Subject post-treatment questionnaire at the end of the treatment (TF).
  - Relevant medical conditions and concomitant medication incl. trade name, dosage, route and start.
  - AE/DD documentation
- 8.3.6 At the final aligner treatment visit  $(T_F)$ , the dentist will complete a final visit worksheet and subject will complete the post-treatment questionnaire.
- 8.3.7 Each subject will receive removable retainers following completion of aligner therapy.

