## 8.8 In-Treatment Period

- 8.8.1 The subject will check in with the Investigator at their dental practice/office monthly (every 4-6 weeks).
  - The Investigator will review the subject's treatment progress and provide feedback to the subject and the Sponsor related to compliance and tracking via completion of a visit worksheet at each visit (T1, T2, T3, etc.).
  - The Investigator will also take subject progress intraoral and extraoral photographs at each check in visit and submit them to the Sponsor.
  - In-treatment subject questionnaire
- 8.8.2 The Investigators and the Sponsor will assess the progression of investigational treatment through information subject submitted to the **eCRF**.

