#### 8.10 Subject Discontinuation

- 8.10.1 The Investigator and/or the Sponsor may discontinuing a subject if severe non-compliance to the protocol. Subject may also be discontinued due to safety reasons as judged by the Investigator and/or Sponsor.
- 8.10.2 If a subject for any reason desires to no longer participate in the study or continue treatment, they are free to discontinue participation in the study, at any time and without providing a reason for the withdrawal. Discontinuation from the clinical study will not affect future treatment /care of the subject.
- 8.10.3 Subjects who discontinue should always be inquired about the reason(s) for their discontinuation and any potential safety issues. If possible, they should be seen and assessed by an Investigator. The termination section in the eCRF should be completed. Safety events should be followed up. Any study specific material provided to the subject should be collected.

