#### 9.2 Secondary Safety Endpoint

The secondary safety endpoint of the study will be the subject self-reported values pertaining to pain/discomfort during treatment and comfort in wearing the aligners captured in the questionnaire. For this endpoint, a Visual Analogue Scale (VAS) with a Wong Baker face scale is used.

- 9.2.1 Subject comfort wearing aligners during treatment via visual analogue scales (VAS): This question is directed to the subject. "How comfortable were the aligners to wear during your treatment?" (VAS: 0 very comfortable 10 very uncomfortable).
- 9.2.2 Subject pain associated with new tooth movements during treatment via visual analogue scales (VAS): This question is directed to the subject.
  "Did you experience any pain associated with new tooth movement?" (VAS: 0 no pain 10 worst possible pain).

**CONFIDENTIAL:** The information in this study protocol is strictly confidential and is available for review to Investigators, study center personnel, the ethics committee, and the health authorities. It will not be disclosed to third parties without written authorization from the Sponsor, except to obtain informed consent from persons receiving the study treatment. Once the protocol is signed, its terms are binding for all parties.

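### Satisfaction (9.4) is rated only when treatment is completed and no rating is required at early discontinuation, so the secondary efficacy endpoint describes completers only

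*Combined protocol and SAP*

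**What the plan says.** **Satisfaction.** Section 9.4 makes subject and dentist satisfaction the secondary efficacy endpoint, scored from 1 (best) to 10 (worst). On timing it says: "This will be assessed through a questionnaire provided to both the dentist and the subject when treatment is completed". The table in 8.3 places the Investigator questionnaire at the final visit alone and has no early-termination column. Sections 8.3.5 and 8.9.1 tie the post-treatment subject questionnaire to the same final visit. Under 8.9.3, participation ends on withdrawal or removal, so no later rating falls due.

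**Discontinuation.** Section 8.10.3 says: "Subjects who discontinue should always be inquired about the reason(s) for their discontinuation and any potential safety issues". It also asks for an Investigator assessment where possible and for the termination part of the eCRF. It names no questionnaire and no rating. Section 16.4.3 keeps withdrawn subjects' data for the planned analyses, but section 12.2 has no rule for a rating that was never taken.

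**Comfort and pain.** Section 9.2 defines the secondary safety endpoint as "subject self-reported values pertaining to pain/discomfort during treatment and comfort in wearing the aligners captured in the questionnaire" and does not limit it to one visit. The other places differ on timing:
- Synopsis: "safety will be assessed through a post-treatment questionnaire administered to the subject asking about subject perceived comfort during treatment"
- 1.2: "Safety will also be assessed through subject questionnaire during and after treatment"
- 8.3.5, every 4-6 weeks: "Completed subject questionnaire at check in visits"
- 8.8.1: "In-treatment subject questionnaire"

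The items on the check-in questionnaire are not listed.

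**The concern.** A rating taken only from people who finish is a rating from a selected group. Slow progress and discomfort are plausible reasons both to stop and to be dissatisfied, and 7.1.1 names both delay and discomfort as more likely with the shorter wear time: "Only wearing aligners for 10-12 hours per day can lead to greater subject discomfort when aligners are worn". Other rules narrow the group further. Section 10.1.3 makes a subject ineligible to continue after any deviation the sponsor has not approved, and section 5.4 pays a second rebate only for compliant, successful completion.

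The report would then give a mean satisfaction that reads as applying to everyone treated but omits those who gave up. A rating not taken at the time of stopping cannot be reliably recovered afterwards. The promise in 16.4.3 has no content for this endpoint, because the plan generates no satisfaction data for subjects who withdraw.

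**Working it through.** **1. The plan's own figure.** Section 12.1.2 gives SD 1, difference 1, two-sided alpha 0.05 and power 90%.
- Normal approximation: n = 2 × (1.960 + 1.282)² × 1² / 1² ≈ 21.0, rounded up to 22 per arm.
- Two-sample t-test: 22.02, rounded up to 23 per arm, with power 0.912 at 23.

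The stated 23 reproduces. It is not tied to satisfaction, so nothing below changes the sample size.

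**2. Ceiling on missing ratings.** Section 4.2 gives 50 per arm and a minimum of 23 completers: (50 − 23)/50 = 27/50 = 54%.

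**3. Error within an arm.** Let completers average m, let a fraction p stop, and let those who stop be d points worse (higher on this scale). The mean in all treated is (1 − p)m + p(m + d) = m + pd. The completers-only mean is m, so it is too favourable by pd. The documents give neither p nor d, so both are assumed here. For d = 1 to 3:
- p = 10%: 0.1 to 0.3 points
- p = 30%: 0.3 to 0.9 points
- p = 54%: 0.54 to 1.62 points

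**4. Error between arms.** With the same d in both arms, the completers-only difference (Nighttime minus Daytime) departs from the all-treated difference by d × (p_test − p_control). A positive value means that the completers-only result flatters Nighttime.

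| Loss, Nighttime | Loss, Daytime | d = 1 | d = 2 | d = 3 |
|---|---|---|---|---|
| 30% | 10% | 0.20 | 0.40 | 0.60 |
| 54% | 20% | 0.34 | 0.68 | 1.02 |
| 10% | 30% | −0.20 | −0.40 | −0.60 |
| 10% | 10% | 0 | 0 | 0 |
| 54% | 54% | 0 | 0 | 0 |

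The sign follows the sign of the difference in loss. With equal loss and equal d the between-arm error is zero, but the error in each arm's mean from step 3 remains. The plan's test is a rank test, so these mean differences show size only and are not the test statistic.

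**5. Comfort and pain, read side by side.** The synopsis names one post-treatment questionnaire. Sections 1.2, 8.3.5 and 8.8.1 and the 8.3 table all have a subject questionnaire during treatment. A subject who stops after the first check-in should therefore already have at least one completed questionnaire; only one who stops before it clearly has none. Two things stay open: whether the 9.2.1 and 9.2.2 items are on the check-in form (9.2.1 is worded as a look back over treatment), and which visit or summary is the endpoint.

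**6. The correlations in 12.2.10.** These pair satisfaction and pain with accuracy of outcome. Accuracy is computed from the actual PAR reduction, which needs the end-of-treatment scan (12.2.4, 12.2.8). A subject who stops without that scan cannot enter them, whatever rating was given.

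**The case against.** The strongest defence has four parts.

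- **Discontinuation is not silent.** Reasons and safety issues are asked, a termination form is completed, 16.4.4 records the primary reason, and adverse events are recorded throughout. This is true, but none of it is a satisfaction score.
- **The 9.4 questions ask about the results achieved.** For a subject who stops in the first weeks, the answer concerns something different from a completer's answer. This stands as a limit on the remedy. It does not justify having no answer.
- **The endpoint is secondary.** It did not drive the sample size, and under 12.2.9 additional between-group tests are optional. This limits the weight of the point.
- **54% is loose.** The 23 must be evaluable and compliant, so a subject who finishes but fails those conditions can still fill in the questionnaire. Subjects withdrawn at treatment-plan review (8.1.7) never receive an aligner. This stands, and the figure is used only as a ceiling.

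A reader might also infer three stronger things that the documents do not support. The first is that subjects who stop leave no comfort or pain rating; the check-in questionnaires contradict this. The second is that the bias runs towards no difference. Section 7.1.1 could mean more stopping on Nighttime, but 7.2.2 and 7.2.3 expect better aesthetics and easier use with that regimen, which could mean more stopping on Daytime, and no loss rates by arm are given. The third is that a rating at discontinuation would repair the correlations in 12.2.10; step 6 of the working shows that by itself it would not.

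**Conclusion.** The point holds for satisfaction. Followed as written, the plan yields a secondary efficacy endpoint in completers only, with at most 54% of an arm unrated while the stated minimum is still met. That each arm's mean would be too favourable rests on the assumption that those who stop are less satisfied. Bias between arms needs, in addition, unequal loss or an unequal penalty; on the assumed figures it runs from zero to about 1 point on the 1-10 scale, and its direction is unknown. For comfort and pain the finding is narrower: in-treatment questionnaires exist, but their items, the time point analysed and the synopsis wording are not aligned. This should be changed because it is cheap and cannot be put right after the fact. It does not threaten the primary analysis or the sample size.

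**What to change.** 1. In 8.10.3 and the 8.3 table, add an early-discontinuation contact at which the subject answers 9.4.2, 9.2.1 and 9.2.2 and the dentist answers 9.4.1, by phone or online if the subject does not attend.
2. In 12.2, analyse satisfaction in all subjects who received an aligner, with completers only as a sensitivity analysis. State how a rating that is still missing will be handled, and report the number missing by arm and reason. Ranking non-responders as worst is one option, but it is a debatable choice of estimand and this point does not depend on it.
3. For comfort and pain, list the check-in items, confirm that they include the 9.2 questions, use those in-treatment ratings for subjects who stop early, and state which visit or summary is the 9.2 endpoint. Reconcile the synopsis with 1.2, 8.3.5 and 8.8.1.

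The cost is four existing questions at a contact 8.10.3 already calls for, one schedule column and a paragraph of analysis text. The downside is small: a rating at discontinuation covers a shorter period and incomplete results, so the time on treatment should be reported beside it.
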